10.2 Analysis Populations

10.2.1 Response-to-treatment populations

All patients who meet eligibility criteria and receive at least one dose of study medication will be included in the main analysis of the response rate, even if there are major protocol deviations (e.g., incorrect treatment schedule or drug administration). Each patient will be assigned to one of the following categories for each response outcome:

TABLE 7: Categories for Response to Treatment

Category	Response
1	Complete response
2	Partial response
3	Stable disease
4	Progressive disease
5	Early death from malignant disease
6	Early death from toxicity
7	Early death from other causes

8	Unknown (not assessable/insufficient data)
---	--

NOTE: By arbitrary convention, category 8 designates unknown status in a clinical database. Patients in response categories 4 to 8 will be considered to have treatment failure (disease progression)

Conclusions are to be based on the population of all eligible patients who receive at least one dose of study medication. Subanalyses will be performed on various subsets of patients, such as those with no major protocol deviations, those who have at least one measure of response after starting treatment or those who continued in the study for the entire treatment period (i.e. did not withdraw prematurely). Sub-analysis will not serve as the basis for drawing conclusions concerning treatment's efficacy.

10.2.2 Safety population

All patients enrolled in the study who receive at least one dose of study treatment will be included in the safety analysis population and considered evaluable for toxicity and safety from the time of their first dose. Analysis will be completed by treatment received rather than treatment assigned. Demographic and baseline characteristics for the safety population will be summarized by number and percent for categorical data (e.g., race/ethnicity) and by descriptive statistics for continuous data (e.g., weight, vital signs, EKG readings, disease status).

10.3 Safety Analysis

10.3.1 Evaluation of adverse events

Treatment-emergent AEs will be translated from investigator terms to a custom medical dictionary and summarized (number and percentage of patients) for each treatment arm for all patients who receive at least one dose. AE summaries will be reported by arm and organized by body system, frequency of occurrence, intensity (i.e., severity grade), and causality or attribution. Patients who experience an AE more than once will be counted only once. The occurrence with the maximum severity will be used to calculate intensity.

10.3.2 Evaluation of serious adverse events and premature withdrawals

AEs deemed serious and those resulting in treatment withdrawal or death will be summarized separately. Narrative paragraphs will be generated to describe the circumstances surrounding each SAE and death.

10.3.3 Extent of exposure

Treatment exposure will be summarized for all patients, including dose administration, number of cycles, dose modifications or delays, and duration of therapy. This will be reported separately by treatment arm.

10.3.4 Early stopping

Stopping rules for excessive toxicity will be incorporated for patients. Excessive toxicity will be defined as removal from treatment due to toxicity despite dose modification. We consider excessive toxicity if more than 25% of subjects have to stop the trial because of toxicity. Once 10 subjects have been enrolled, we will continually monitor the rate of toxicity withdrawal and stop if we have evidence that the rate is above 25%. If the rate is >25% at any time after 10

patients are accrued, enrollment will be halted and re-evaluated for dose reduction or closed to accrual.

10.3.5 Statistical procedures

Summary statistics include the number of observations, mean, standard deviation, median, minimum, and maximum values. As this is not a comparative trial, p-values will be used sparingly.

10.3.6 Sample size calculation

The statistical design for DRPro will be an Optimal Simon 2-stage Phase II. Based on the TOPARP-A study the null response rate for DRPro is 6% and a response rate of 6% or less would not be interesting. Accrual of 35 DRPro patients will provide 80% power to detect a response rate of 20% or greater with 5% type I error. Stage 1 will accrue 17 DRPro patients. If 1 or less DRPro patients have a preliminary response (CR/PR using radiographic by RECIST v.1.1 or PSA decline $\geq 50\%$) then the DRPro cohort will stop. If 2 or more responses occur, then the 2nd stage will begin and another 18 DRPro patients will be accrued. If 5 or more patient responses are seen out of the 35 DRPro patients, then the combination treatment will be deemed interesting for further study in the DRPro population.

The statistical design for the DRDef is a Mini-Max Simon 2-stage Phase II. Based on a response rate of 45% within the first 12 weeks in TOPARP-A, a response rate of under 45% would not be interesting. Stage 1 of this design requires 12 DRDef patients and if 5 or less patients have a preliminary response (CR/PR using radiographic by RECIST v.1.1. or PSA decline $\geq 50\%$), then the DRDef cohort would not be of interest. If 6 or more patients do respond, this would support consideration to expand (with amendment or new protocol) with another 13 patients (to a total of 25 patients) or a completely separate trial. Accrual of 25 patients would provide 80% power to detect a response rate of 70% or greater with 5% type I error. If 16 or more patient responses were seen in a 25 total DRDef patient cohort, then the combination treatment would be deemed interesting for further study DRDef. Different RR are used for DRDef and DRPro as different expected baseline RR.

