Patients with progressive, metastatic, castration-resistant prostate cancer who received a) at least one line of systemic therapy for mCRPC or b) failed ongoing second generation anti-hormonal therapy (e.g. abiraterone) in the hormone-sensitive or non-metastatic castration resistant phases of disease. They must remain on continuous LHRH agonist/antagonist, unless they have undergone orchietomy.

Duration of treatment

Patients must have washed out of any prior systemic therapy for either 3 weeks or 5 half-lives (whichever is longest), excluding prednisone, LHRH agonist/antagonists, bisphosphonate or RANKL inhibitor. The median duration of study per patient is estimated to be approximately 12 months.

Investigational product, dosage and mode of administration

Olaparib, 300 mg by mouth, twice a day, days 1-28 of a 28-day cycle.
AZD6738, 160 mg by mouth, daily, days 1-7 of a 28-day cycle.

Statistical methods

For the DRPro population (characterized through study sequencing or previously completed), using an Optimal Simon 2-stage design, this cohort will be 35 total patients with an interim for futility after 17 DRPro patients have been accrued. If 2 or more responses are seen in the first stage, then the second stage will open and accrue 18 more DRPro patients. If 5 or more patient responses are seen out of the 35 DRPro patients, then the combination treatment will be deemed interesting for further study in a DRPro population. The null response rate from the

TOPARP-A study is 6%. The current design will detect at 80% power, a response rate of 20% or greater with 5% one-sided type I error.

For the DRDef population (characterized through study sequencing or previously completed), using a Mini-Max Simon 2-stage design. A set of 12 DRDef will be treated and if 6 or more responses are seen, this would support consideration to expand (with amendment or new protocol) with another 13 patients or a completely separate trial.

Principal analyses will report the response rate (CR/PR) per radiographic response according to RECIST v1.1 or PSA ($\geq 50\%$ decline) in DRPro and DRDef patients. The cohorts will be separated for all efficacy analyses.

TABLE OF CONTENTS		PAGE
	TITLE PAGE	1
	TABLE OF CONTENTS	6
	LIST OF ABBREVIATIONS AND DEFINITION OF TERMS	11
1.	INTRODUCTION.....	14
1.1	Background.....	14
	1.1.1 Pre-clinical experience.....	15
	1.1.2 Toxicology and safety pharmacology summary	15
	1.1.3 Clinical experience.....	16
1.2	Research Hypothesis	16

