Precision oncology (matching tumor specific genetic changes to drugs targeting those alterations/pathways) is revolutionizing cancer care. Preliminary results have shown this strategy may be effective in prostate cancer by targeting DNA repair pathways. Approximately 20% of mCRPC patients have germline or somatic loss of DNA repair genes (dominated by BRCA2, ATM) rendering them DNA repair deficient (DRDef) [2]. Targeting this DRDef population with poly (ADP-ribose) polymerase (PARP) inhibitors has shown promise in two phase II studies. The first was an unselected trial where DRDef patients were uniquely sensitive to olaparib (a PARP inhibitor) resulting in an 88% response rate (based on CTC number, radiographic and PSA effects). DNA repair defect negative (DRPro) patients had only a 6% response rate [3]. A separate trial suggests activity, but wasn't designed or powered towards that hypothesis. When treated with abiraterone, prednisone and veliparib (a PARP inhibitor), 12 of 13 (92.3%) DRDef patients had a PSA decline of >50% and 10 of 11 (90.9%) DRDef patients with measurable disease had a RECIST response. This compares favorably to DRPro patients who had a 64.7% PSA response rate and 40% RECIST response to the same combination [4]. Finally, retrospective analysis of excellent responder patients treated with platinum agents (cisplatin or carboplatin) also found them to be DRDef (BRCA2 carriers), further supporting targeting DNA repair in this population. [5].

The problem remains, that only 20% of mCRPC patients are DRDef. To simulate this genomic requirement, combinations of DNA repair targeting agents have been attempted. Cisplatin and cisplatin/gemcitabine were combined with olaparib but hematologic toxicity was limiting [6, 7]. Carboplatin and carboplatin/paclitaxel were combined with a PARP inhibitor (rucaparib or olaparib) with a better tolerability profile, but unknown benefit [8, 9]. Various carboplatin combinations remain in clinical study. Although small in number, responses seen in these early clinical trials remain in DRDef patients. The 80% DRPro patients in prostate cancer remain without a proven DNA targeting regimen.

Ataxia telangiectasia and Rad3-related protein (ATR) is an attractive DNA repair target candidate due to its involvement in cell cycle checkpoint regulation, stalled replication fork resolution, single strand break repair (with Replication Protein A) and double strand break

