7.6.8 Evaluation of best overall response

The best overall response is the best response recorded from the start of the treatment until disease progression/recurrence (taking as reference for progressive disease the smallest measurements recorded since the treatment started). The patient's best response assignment will depend on the achievement of both measurement and confirmation criteria.

TABLE 5 Best Overall Response For Patients with Measurable Disease (i.e. Target Disease)

Target Lesions	Non-Target Lesions	New Lesions	Overall Response	Best Overall Response when Confirmation is Required*
CR	CR	No	CR	≥4 wks. Confirmation
CR	Non-CR/Non-PD	No	PR	≥4 wks. Confirmation
CR	Not evaluated	No	PR	
PR	Non-CR/Non-PD/not evaluated	No	PR	
SD	Non-CR/Non-PD/not evaluated	No	SD	Documented at least once ≥4 wks. from baseline
PD	Any	Yes or No	PD	No prior SD, PR or CR
Any	PD**	Yes or No	PD	
Any	Any	Yes	PD	

* See RECIST 1.1 manuscript for further details on what is evidence of a new lesion.
** In exceptional circumstances, unequivocal progression in non-target lesions may be accepted as disease progression.

Note: Patients with a global deterioration of health status requiring discontinuation of treatment without objective evidence of disease progression at that time should be reported as “*symptomatic deterioration*.” Every effort should be made to document the objective progression even after discontinuation of treatment.

Table 6 Best Overall Response for Patients with Non -Measurable Disease (i.e., Non-Target Disease)

Non-Target Lesions	New Lesions	Overall Response
CR	No	CR
Non-CR/Non-PD	No	Non-CR/Non-PD*
Not all evaluated	No	Not evaluated
Unequivocal PD	Yes or No	PD
Any	Yes	PD

* ‘Non-CR/non-PD’ is preferred over ‘stable disease’ for non-target disease since SD is increasingly used as an endpoint for assessment of efficacy in some trials so to assign this category when no lesions can be measured is confusing.

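### The 45% DRDef benchmark is a 12-week response rate, but the responses counted towards 6 of 12 have no 12-week limit

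*Combined protocol and SAP*

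**What the plan says.** **The benchmark.** Section 10.3.6: "Based on a response rate of 45% within the first 12 weeks in TOPARP-A, a response rate of under 45% would not be interesting". TOPARP-A is the olaparib-alone comparator: the synopsis takes its 6% null rate for repair-proficient patients from that study, and section 1.1 reports the same 6% from the unselected olaparib trial.

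**The rule.** "The statistical design for the DRDef is a Mini-Max Simon 2-stage Phase II". "Stage 1 of this design requires 12 DRDef patients and if 5 or less patients have a preliminary response", the cohort is not of interest. Six or more responses would support considering expansion by 13 patients, by amendment or new protocol, or a separate trial. For the expanded cohort the success cut-off is 16 of 25: "Accrual of 25 patients would provide 80% power to detect a response rate of 70% or greater with 5% type I error".

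**The response that is counted.** The synopsis and sections 2.2, 10.1.2 and 10.3.6 describe DRDef response as RECIST CR/PR or a PSA fall of at least 50%, and none sets a latest date. Section 7.6.8 on RECIST response: "The best overall response is the best response recorded from the start of the treatment until disease progression/recurrence". Section 7.6.7.4 requires a PSA response to be confirmed at least 4 weeks later, but does not say by when it must first occur. Section 10.3.6 calls the stage 1 responses preliminary without defining that in time. Section 7.6.1 mentions PSA change at 12 weeks as something to report, next to the maximum fall at any point; neither is tied to the 6-of-12 rule.

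**The concern.** The cohort has one arm, and olaparib, half of the regimen, is already described in sections 1.1 and 1.3 as active in DRDef disease. The 45% is therefore the only thing in the plan that separates a gain from the combination from what olaparib does alone. If the benchmark is a 12-week rate and the trial counts later responses too, some of the apparent gain can come from the longer clock. What is at stake is the decision to consider expanding the DRDef cohort and, if it is expanded on the stated cut-offs, the 5% error rate that section 10.3.6 attaches to them.

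**Working it through.** **Inputs.** From section 10.3.6: null rate 0.45, alternative 0.70, 12 patients in stage 1 (continue on 6 or more), 25 in total (success on 16 or more), 5% type I error, 80% power. The test is taken as one-sided. The synopsis says so only for the repair-proficient cohort ("a response rate of 20% or greater with 5% one-sided type I error"), and the same is assumed here.

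**Formulas.** With true response rate p:

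- Gate: G(p) = Σ C(12,x) pˣ (1−p)¹²⁻ˣ, for x = 6 to 12.
- Full rule: S(p) = Σ P(X₁ = x) · P(X₂ ≥ 16 − x), for x = 6 to 12, with X₁ ~ Bin(12, p) and X₂ ~ Bin(13, p).

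**Step 1: the plan's own figures.**

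- G(0.45) = 0.2124 + 0.1489 + 0.0762 + 0.0277 + 0.0068 + 0.0010 + 0.0001 = 0.473.
- S(0.45) = 0.00432 + 0.01040 + 0.01362 + 0.00987 + 0.00390 + 0.00078 + 0.00006 = 0.043, inside the 5% ceiling.
- S(0.70) = 0.804, matching the stated 80%.
- An exhaustive search for the minimax design at these inputs returns the stated one (6 of 12, then 16 of 25).

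The design arithmetic is correct. The question is only what the 45% measures.

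**Step 2: do the two clocks differ under the trial's schedule?** The study calendar puts scans every 8 weeks from C1D1 for the first three timepoints (about weeks 8, 16 and 24), then every 12 weeks. Only the week-8 scan is scheduled inside a 12-week window. (Section 7.6.7.3 mentions a 12-week bone-scan reading, but it grades scans as stable or worse and gives no RECIST response.) PSA is drawn on Day 1 of each cycle, and C4D1 falls 3 × 28 = 84 days, or 12 weeks, after C1D1. A response first seen on the week-16 scan, or on a PSA after C4D1, can count here but lies outside the window given for the benchmark.

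**Step 3: direction.** Every patient who responds within 12 weeks is also an any-time responder, so in the same patients the any-time rate is at least the 12-week rate. Both G and S rise with p.

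**Step 4: size.** The documents give no any-time olaparib-alone rate for RECIST or PSA response, so the rates above 45% are assumptions.

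| Any-time rate on olaparib alone, no gain from the second drug | At least 6 of 12 | Full rule, 16 of 25 (only if expanded) |
|---|---|---|
| 45% (clocks matched) | 0.473 | 0.043 |
| 50% (assumed) | 0.613 | 0.112 |
| 55% (assumed) | 0.739 | 0.238 |
| 60% (assumed) | 0.842 | 0.418 |

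The part of the gate probability that belongs to the mismatch is the increment: 0.613 − 0.473 = 0.140 at 50%, up to 0.842 − 0.473 = 0.369 at 60%.

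**The case against.** Several points on the other side stand, and they limit what can be claimed.

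- **The gate is permissive anyway.** At a true 45% on a matched clock, 6 of 12 is reached 47% of the time. A reader might infer that the longer clock is why the gate can be passed without benefit; only the increment above 0.473 can be charged to it.
- **The 25-patient rule is not run here.** Of the 47 evaluable patients in the synopsis, 35 are repair-proficient, which leaves 12. A reader might infer that this trial's type I error is inflated; that holds only if a later amendment or protocol keeps the stated cut-offs.
- **The secondary objective is estimation.** Section 10.1.2 reports the DRDef rate with a 95% confidence interval and no test against 45%. A reader might infer that the objective itself compares two windows; only the decision rule does.
- **The 88% in section 1.1 is not an upper bound.** That figure is described as "resulting in an 88% response rate (based on CTC number, radiographic and PSA effects"). It includes circulating tumour cell response, which this endpoint excludes, and no window is given. A range of 45% to 88% for the any-time rate is not supported.
- **The extra time per patient is unknown.** The synopsis says "The median duration of study per patient is estimated to be approximately 12 months". A reader might subtract 12 weeks and infer about nine further months in which to respond. The figure covers all patients and is not time to progression in DRDef, where best response closes.
- **The net bias of the whole comparison is not established.** Confirmed PSA response, counting unassessed patients as non-responders (section 7.6.3) and admitting monoallelic ATM loss could each move the rate, and the documents do not say whether the benchmark shared them.
- **The gate's clock is partly a matter of silence.** Section 7.6.8 is explicit for RECIST best response. For PSA, and for the preliminary responses of stage 1, the plan simply gives no window.

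None of this supplies a 12-week limit for the trial's response or removes it from the benchmark. The 12-week PSA change in section 7.6.1 would allow a matched PSA reading, but the rule does not use it.

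**Conclusion.** The point holds in a limited form. The 45% is a 12-week rate, the counted response has no 12-week limit, and for the time window alone the mismatch can only make the gate easier to pass with no gain over olaparib. The direction follows by logic; the size rests on an assumed excess of 5 to 15 points, for which the documents offer no figure. On that assumption the gate's pass probability with no gain is 0.61 to 0.84 instead of 0.47, and the hypothetical false-positive chance of an unchanged 16-of-25 rule is 0.11 to 0.42 instead of 0.043. DRDef is a secondary cohort and 6 of 12 commits nobody to expansion, so this does not affect the primary conclusion. It is still worth correcting, because the decision rule uses the benchmark and the data needed to match the clocks are already scheduled.

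**What to change.** In section 10.3.6, with a matching line in 10.1.2, apply the 6-of-12 rule, and any later 16-of-25 rule, to responses first documented within the first 12 weeks. State which assessments count:

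- PSA through C4D1, with its visit window.
- The week-8 scan, with its window.
- Whether the week-16 scan enters a sensitivity count, since the calendar has no scan at week 12.
- That confirmation may fall after week 12.

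Report the any-time response rate separately and do not read it against 45%.

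The alternative is to keep any-time response, justify an any-time null rate for olaparib alone on this endpoint, and recompute the cut-offs.

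**Cost.** A few sentences and no new assessments. The downside of the first option is that late responders, and radiographic responses arising between weeks 8 and 12, would not count towards the expansion decision. The second group is a loss relative to a true 12-week benchmark and could work against the combination, which is why the handling of the week-16 scan should be settled in advance. Both groups would still appear in the any-time rate.

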10.3.7 Derived variables

- Change from baseline will be calculated as the rating after baseline minus the rating at baseline
- Percent change from baseline will be calculated as the rating after baseline minus the rating at baseline quantity divided by the baseline.
- Duration of treatment will be defined as the number of days from the first day of protocol assigned intervention to the last day of protocol treatment. If the last day of protocol treatment is missing, the date of the last visit will be substituted for the missing value

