5. STUDY CALENDAR

	Screening (Day -42 to Day -1)	Cycle 1 ^m , 2 ^m		Cycle 3+ Day 1 ^m (-5 to +3d)	End of Treatment, 30 (±3) Day FU ^m	Long- term FU ^j
		Day 1 ^m (±3day for c2)	Day 8 ^m (±3 day)			
Informed Consent	X					
Medical/Surgical History, Demographics, Height Prior Histology (either report or clinician note as source)	X					
Biopsy of Metastatic Disease	X ^a					
Peripheral blood for germline and/or circulating tumor DNA	X ^b					
PE, Vitals ⁱ , Weight	X	X ^m	X ^m	X ^m	X ^m	
Performance Status	X	X	X	X	X	
Adverse Event, Toxicity Evaluations		X	X	X	X	
Medication Review	X	X	X	X	X	
Study Drug ^c		X	X	X		
Radiologic evaluations and measurements ^d	X (Must be ≤4 weeks from C1D1 or repeated) ^k			X ^e		
ECG	X (triplicate)	X ^g (C1D1 only)				
Serum Chemistry ^f , LDH	X	X	X (optional C2D8)	X	X	
PT (INR), APTT, Urinalysis ^h	X					
CBC with Differential	X	X	X (optional C2D8)	X	X	
PSA	X	X		X	X	

	Screening (Day -42 to Day -1)	Cycle 1 ^m , 2 ^m		Cycle 3+ Day 1 ^m (-5 to +3d)	End of Treatment, 30 (±3) Day FUm	Long- term FU ⁱ
		Day 1 ^m (±3day for c2)	Day 8 ^m (±3 day)			
Testosterone	X					
Circulating Correlatives		X ⁿ		C3D1 only ⁿ	X ⁿ	
Long-term follow- up for MDS/AML or new primary malignancy reporting						X

a. Biopsy must be done after patient has consented and registered to the study (unless pre-existing, CLIA certified lab, next-generation sequencing of metastatic mCRPC biopsy has been completed or mCRPC tissue available to submit for testing). Submitted tissue must be deemed adequate or fully reported prior to starting therapy.

b. Peripheral blood is sent for either germline comparison (if tissue also completed) or exploratory analysis of circulating tumor DNA and germline DNA if biopsy failed or is unsafe (and analysis available). If the biopsy is attempted and has insufficient tissue, new blood may not need to be redrawn as it was sent with biopsy.

c. For drug schedule see Section 1.2.

d. Radiographic evaluation will include radionuclide bone scan, CT or MRI of abdomen and pelvis, and CT, CXR or MRI of the chest as appropriate. All disease sites must be assessed using the same methodology as performed at baseline. At the discretion of the investigator, additional radiological evaluations may be performed at an unscheduled time point.

e. While receiving therapy, radiologic tests are performed every 8 weeks (±1 week) from C1D1. After the third scanning timepoint (~6 months), radiologic tests are performed every 12 weeks (±1 week) from C1D1.

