5.3.3 Agent administration + distribution

All treatment is rendered on an outpatient basis. Reported side effects and potential risks are described in Section 6.1/6.2 and dose modifications in Section 5.4. No other investigational or commercial agents or therapies other than those described below may be administered with the intent to treat the patient's malignancy (excluding LHRH agonists/antagonists). The research staff will provide detailed instruction and training for the handling of study drugs and administration at the beginning of the study to each patient. All dosages prescribed and dispensed to the patient and all dose changes during the study are recorded. The patient should contact the Investigator if he is unable to take the study drugs as prescribed.

Study drug may be shipped by each site's research pharmacy (if they are able to) via certified temperature-controlled container for overnight delivery, with tracking number and delivery signature required. Consultation with local research pharmacy is required and coordinating center must be notified that the local IRB and site is able to do this PRIOR to implementing site-> subject shipments. Sites are required to submit to coordinating center the subject diary and associated shipment processes for each cycle. The drug dispensation log must be updated as required noting direct shipment and copy of signature of receipt is encouraged to be obtained (if possible), placed in study records and be available for monitoring. Any non-receipt by subject/household must be reported to study staff locally so that shipment can be tracked and drug accounted for. Any missed dose of study medication is to be managed per protocol.

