5.4 Management of Toxicity

5.4.1 Toxicities that require discontinuation from protocol therapy

Any toxicity observed during the course of the study should be managed in the first instance by interruption of the dose of study treatment and dose reductions if necessary. Repeat dose interruptions are allowed as required for a maximum of 28 days on each occasion. Treatment must be interrupted until the patient recovers completely or the toxicity reverts to NCI CTCAE grade 1 or 2 (depending on toxicity) or to the baseline CTCAE grade. If the required interruption is any longer than 28 days due to toxicity, the patient must be removed from the study. If at any point during study treatment, it becomes apparent that the tumor is not coming under control, patients are to be removed from study and treated as clinically indicated.

Protocol therapy should be discontinued if a patient experiences:

- Any CTCAE Grade 4 toxicity with the exception of:
 - CTCAE Grade 4 neutropenia of 5 days or fewer duration
 - CTCAE Grade 4 nausea, vomiting or diarrhea that resolves to Grade 3 in less than 72 hours in patients who have not received optimal anti-emetic or anti-diarrheal therapy
 - CTCAE Grade 4 laboratory abnormalities that can be readily corrected within 72 hours and do not result in hospitalization
- CTCAE Grade 3 or 4 thrombocytopenia with bleeding requiring hospitalization

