5.5 Treatment Compliance

To safely participate in a clinical study, all patients should complete pill diaries and planned laboratory studies. Unused drug will be returned to the study team who will contact the sponsor for instruction or follow local standard operating practices.

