5.6.2 Duration of follow-up

Patients will be followed for 30 days after removal from treatment or until death, whichever occurs first. Patients removed from treatment for unacceptable adverse events will be followed until resolution or stabilization of the adverse event.

All patients should be followed for MDS/AML and new primary malignancy assessment for up to 5 years after the patient completes the study per Section 7.7.1.

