chart review for the diagnosis or b) phone call asking the patient whether they have been diagnosed with MDS/AML or a new malignancy (one of these should happen between months 10-12 after discontinuation). If a patient has been diagnosed with MDS/AML or another malignancy, a questionnaire may be sent to them for further information. This will continue for 5 years after a patient completes study.

At any time after a patient has completed the study, if an Investigator learns of any SAE including sudden death of unknown cause, and he/she considers there is a reasonable possibility that the event is causally related to the investigational product, the investigator should notify the Principal Investigator who will notify AstraZeneca, Patient Safety.

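### A missing last treatment date is replaced by the date of the last visit, which may be the off-drug 30-day follow-up; the substitute should be the last documented dose

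*Combined protocol and SAP*

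**What the plan says.** Section 10.3.7 (Derived variables) defines duration of treatment as "the number of days from the first day of protocol assigned intervention to the last day of protocol treatment". It then gives the rule for missing data: "If the last day of protocol treatment is missing, the date of the last visit will be substituted for the missing value". The term last visit is not defined there or elsewhere.

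The study calendar (Section 5) has a final clinic column headed "End of Treatment, 30 (±3) Day FU". Examination, laboratory tests, PSA and adverse-event review are marked in it, but the study-drug row is empty. Section 5.6.2 adds: "Patients will be followed for 30 days after removal from treatment or until death, whichever occurs first". A separate long-term column covers surveillance for MDS/AML and new malignancy, which Section 7.7.1 carries out by annual chart review or telephone call: "This will continue for 5 years after a patient completes study".

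Other sections provide records of when drug was taken. Section 5.3.3 says: "All dosages prescribed and dispensed to the patient and all dose changes during the study are recorded". Section 5.5 says that "all patients should complete pill diaries and planned laboratory studies". Sections 5.4.2 and 5.4.13 send interruptions and missed doses to the eCRF, and Sections 6.1 and 6.2 require accountability logs.

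**The concern.** The fallback does not estimate the quantity the section defines. The definition ends at the last day on drug. The substitute ends at the last day the patient was seen, and the calendar places a clinic visit about a month after drug has stopped. For a patient who attended that visit, the substitution counts an off-drug month as exposure.

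Treatment exposure by genetic subtype is part of the named safety outcome measure (Section 2.3), and it is summarised again in Sections 10.1.2 and 10.3.3. Longer reported exposure can be read as better tolerability. The DRDef cohort has only 12 patients, and the summary statistics in Section 10.3.5 include the maximum, so one imputed value could be visible in a table.

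**Working it through.** The plan gives no figure for treatment duration, for the proportion of missing stop dates or for the resulting error, so there is nothing to reproduce. The check is of the size and direction of the error.

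**Inputs from the documents**
- Follow-up window: 30 ± 3 days, so 27 to 33 days (study calendar).
- Patients: 47 in all (synopsis), made up of 35 DRPro and 12 DRDef (Section 10.3.6).
- Cycle: 28 days, with olaparib on days 1 to 28 (Section 5.3.2). From Cycle 3 there is one scheduled visit per cycle, on Day 1 (calendar).
- Interruptions: "Repeat dose interruptions are allowed as required for a maximum of 28 days on each occasion" (Section 5.4.1).
- Median time on study: about 12 months (synopsis). This is the only duration estimate given.

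**Error for one imputed patient** = last visit date − true last dose date.
- Attended the 30-day visit, counted from last dose: +27 to +33 days.
- The same, but counted from removal after a full 28-day interruption: 27 + 28 = 55 to 33 + 28 = 61 days. Section 5.6.2 counts from removal; Sections 5.6.1 and 7.7.1 count safety follow-up from the last dose.
- Lost after a Day 1 visit in Cycle 3 or later, but took olaparib to the end of the cycle: 1 − 28 = −27 days. This assumes the patient held a full cycle's supply.

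**Relative size for a patient who gains 27 to 33 days**
- 12 months of treatment (365 days): 27/365 = 7% to 33/365 = 9%.
- Three cycles (84 days, assumed): 27/84 = 32% to 33/84 = 39%.
- Two cycles (56 days, assumed): 27/56 = 48% to 33/56 = 59%.

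**Shift in the cohort mean** = 30 × k/N, where k is the number of patients with a missing date who attended the 30-day visit. The value of k is not in the documents, so a range is shown.

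| k of N | Shift in mean (days) |
|---|---|
| 1 of 47 | 0.6 |
| 5 of 47 | 3.2 |
| 9 of 47 | 5.7 |
| 47 of 47 | 30 |
| 1 of 12 (DRDef) | 30/12 = 2.5 |

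**Shift in the median.** This was simulated with N = 47 and assumed exponential durations with medians of 3, 6 and 12 months, adding 30 days to each affected patient. The median moved by about 0.6 to 0.7 days with 2% of patients affected, 1.6 with 5%, 3 with 10% and 6.5 with 20%. The mean and median therefore tell the same story.

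**The case against.** The strongest reply is that the rule will rarely operate, and that when it does the harmful case is unlikely. Diaries, dispensing entries, drug returns and eCRF interruption records should supply most stop dates, and Section 7.1 requires incomplete data to be queried and resolved. A site that schedules a visit 30 days after the last dose would normally know when that dose was taken. Patients who disappear are the ones most likely to lack a stop date, and they are also the least likely to attend the follow-up. All of this is fair, and it keeps the point small. It does not rescue the rule, which still names the wrong substitute whenever it is used, while the records cited in its defence are the better source.

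Three stronger readings are tempting, and the documents do not support them:
- **That reported duration as a whole is overstated by about a month.** The rule applies only to missing dates. A 30-day shift in the mean would need all 47 dates to be missing.
- **That the error always lengthens exposure.** This holds only for patients seen after stopping. A patient lost between Day 1 visits can have up to about four weeks omitted.
- **That a long-term contact could add months or years.** These contacts are chart reviews or calls in a separate calendar column, and nothing calls them visits. The rule does not exclude them, which is a reason to name them in the fix, but the large error is speculative.

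**Conclusion.** The rule in Section 10.3.7 conflicts with the section's own definition of duration. For a patient with a missing stop date who attended the 30-day follow-up, it adds about 27 to 33 off-drug days. For a patient lost before that visit, it may subtract days. The net direction across the cohort cannot be settled from the documents.

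For the patients whose duration is lengthened, the effect on the mean is about 30 days times their share: under one day if a single patient of 47 is affected, about three days if five are, and 2.5 days for one DRDef patient. These figures assume that the follow-up visit falls 30 days after the last dose and that k takes the values shown.

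The consequence is confined to the descriptive exposure summary. The response rate, the Simon two-stage rules and the progression-free survival endpoints do not use this variable. The toxicity stopping rule in Section 10.3.4 does not use it either, since it counts withdrawals. The point is worth correcting because exposure is a named safety outcome, but it is minor.

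**What to change.** Replace the fallback sentence in Section 10.3.7 with an ordered rule:

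1. If the last treatment date is missing, use the last dose documented in the pill diary, the drug accountability record or the eCRF.
2. If none of these gives a date, use the last visit at which the patient was recorded as on study drug.
3. Do not use the 30-day follow-up or any long-term contact.
4. Report, by cohort, how many dates were imputed and by which step.

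Step 2 can still understate exposure for a patient lost between visits, and the count in step 4 lets the reader judge how much that matters.

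The cost is a short text change and a little extra data work on records already kept. No patient procedure changes. Reported durations may come out slightly shorter.
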